Substance abuse costs our nation over \$600 billion annually. Drug addiction treatment reduces drug use and has been shown to reduce the health and societal cost far more than the actual cost of the treatment. Treatment is also much less expensive than other options. Outcomes of drug treatment programs are dependent on adequate treatment length and drop out is one of the major problems in the current treatment program. It is therefore critical to optimize drug dosing regimens in patients to improve adherence and success of the treatment programs. In 2012, an estimated 400,000 adults aged 18 or older were current illicit drug users. Many of these were pregnant women. In the most recent National Survey on Drug Use and Health (2012), 6% of pregnant women reported using illicit substances within the past 30 days¹. Azadi et al found that 3% of women were urine-positive for illicit opioids at the time of delivery². Currently, the standard of care for an opioid-dependent pregnant woman in most institutions is methadone, however buprenorphine (BUP) is also used for this indication as it is FDA-approved for opioid addiction although not specifically for pregnant women. There has been increasing evidence that BUP may have comparable efficacy to methadone, and may have fewer severe neonatal complications especially neonatal abstinence syndrome (NAS). In a recent study, BUP-exposed, as opposed to methadone exposed, neonates required significantly less morphine for treatment of NAS, had significantly shorter duration of treatment for NAS and had significantly shorter hospital stays³. Methadone, a full μ agonist, has significant adverse reactions such as Q-T prolongation, potential for life-threatening respiratory depression and extreme sedation⁴⁻⁶. Conversion from illicit narcotic use to methadone commonly requires hospitalization for 3-4 days as the dose of methadone is titrated upward based on the patient's symptomatology^{4,5}. Upon hospital discharge methadone treated patients receive daily dosing of medication at outpatient clinics that monitor the patients for continued illicit drug use. This requirement is extremely burdensome on the patients since many do not have transportation and they must arrive at the clinics in the morning. BUP, a partial μ agonist, has decreased severity of adverse reactions and therefore physicians are able to convert patients on an outpatient basis. The patient is given a 1-4 week supply of oral medication thus eliminating the burdensome task of attending daily clinics for drug administration. These benefits of BUP are changing the management of drug addiction dramatically and more institutions will turn from in-patient treatment with methadone to the outpatient strategy with BUP. The American College of Obstetricians and Gynecologists in its 2012 Committee Opinion indicates that the literature "supports the use of buprenorphine as first line treatment for pregnant opioid –dependent women"⁷. Similarly the American Society of Addiction Medicine supports the use of buprenorphine in opioid- addicted pregnant women⁸ and the World Health Organization (WHO) which encourages availability of a buprenorphine option has described the worldwide availability of buprenorphine⁹. The dosing of BUP currently is based on studies in men and non-pregnant women and limited animal data that related plasma concentrations of BUP to the degree of saturation of the μ receptor in the brain¹⁰⁻¹³. These studies suggest that a dose of 16 mg daily saturates 95% of the μ receptors. The plasma half-life in non-pregnant subjects is approximately 22 hours and therefore a dose of 16 mg/day appears to be sufficient to saturate the receptors. The standard recommended dosing regimen for sublingual BUP is therefore 8 mg bid or 16 mg QD. Unlike for methadone, where increased dosing is recommended during pregnancy, currently there are no guidelines on dosing BUP in pregnant women. The dosing regimen used in non-pregnant subjects does not appear to be adequate for pregnant women. Dosing is adjusted to the patient's symptomatology using the Clinical Opiate Withdrawal (COW) score, some of which is subjective and some based on objective physiological parameters. The failure rate for BUP is highest (33%) during the induction period i.e. the time from stopping illicit drug use to the point of achieving a stable dose of BUP³. This suggests that the current treatment regimens for BUP are inadequate for many women. Indeed at Magee-Womens Hospital, using COW scores to determine a dosing regimen has resulted in many women requiring doses higher than the 16 mg daily dose used in non-pregnant subjects. The high failure rate of BUP during induction and the experience at Magee are

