We will define the pharmacokinetics of buprenorphine and determine if there is a better way to gauge dosing based on objective, physiological parameters of satiety. We will also determine which maternal, placental or fetal factors impact the risk of Neonatal Abstinence Syndrome (NAS) and will define neonatal exposure to buprenorphine through breast milk.

Our specific aims are:

1. To determine the impact of pregnancy on the pharmacokinetics of buprenorphine (BUP) and its metabolites after sublingual administration.
2. To determine the impact of patient covariates such as age, race, co-medications and single nucleotide polymorphisms of BUP metabolizing enzymes (CYP3A4/5; UGT) and transporters (P-glycoprotein) on the variability in exposure of BUP and its metabolites in pregnant women.
3. To evaluate potential pharmacodynamic endpoints for dosing sublingual BUP during pregnancy and the non-pregnant state.
4. To evaluate the relationship between maternal and umbilical cord BUP and its metabolite concentrations.
5. To evaluate the relationship between maternal, placental and neonatal covariates such as concentrations of BUP and its metabolites in maternal and umbilical cord blood and maternal and newborn hair to NAS severity and duration.
6. To evaluate potential infant exposure to BUP and metabolites through breast milk.

We anticipate that the currently recommended dose of buprenorphine will be insufficient in many women to satisfy their drug cravings. Although some part of this craving may be psychological rather than physiologic, we anticipate that alterations in physiology due to pregnancy may result in more rapid metabolism and elimination of this medication and thus provide a level of medication that is sub-therapeutic. We also anticipate that the poor relationship between NAS and maternal dosage of buprenorphine may in part be explained by maternal or placental factors which impact fetal exposure.

D. Approach - Overall Strategy Methodology and Analysis

D.1. Study Overview

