Maternal cotinine and catecholamines will also be measured in the blood and related to the physiologic variables and to maternal craving scores. A maternal hair sample will be obtained around the time of delivery when possible for determination of buprenorphine and metabolite content. Pharmacokinetic modeling will be performed for both the parent compound and its major metabolites. We will determine the impact of the CYP and UGT SNPs on plasma and umbilical cord blood concentrations of BUP and its metabolites.

We will also seek to enroll subjects in an elective ancillary study to determine how rapidly the metabolizing enzyme activity changes after delivery. For those agreeing, we will collect 1-2 maternal blood samples at least 2 days apart while the patient is in the hospital. We will continue to collect weekly maternal blood samples during the subject's routine visits to the MWH BUP clinic for 4 weeks.

For Specific Aims 2, 4 and 5:

Blood will be obtained and genotyping of enzymes responsible for the metabolism of BUP (CYP3A and UGT) will be performed. Given that norbuprenorphine is a substrate for P-glycoprotein (P-gp), genotyping for Pgp will also be performed. We will also evaluate peripheral blood mononuclear cells (PBMCs) as a surrogate marker of metabolic enzymes and transporters. The expression of drug metabolizing enzymes and transporters in the PBMCs will be correlated with the plasma concentrations of BUP and its major metabolites.

Those women who do not participate in the PK study described in the section above (for specific aims 1 and 3) will be consented to participate in some or all of the other components of the study. In those women, we will obtain a blood specimen at the time of consent and record the time of blood draw, the time of the last dose administration, and the dosing history. Subjects recruited to the other components of the study will not reduce the sample size requirements (n=40) for the parent trial but will be used to more precisely model BUP pharmacokinetics.

The following applies to all enrolled women whether or not they are participating in the PK study.

- A maternal blood sample will be obtained from the mother prior to delivery. A portion of the placenta, umbilical cord, and umbilical cord blood will be collected at delivery and immediately frozen.

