No attempt will be made to mandate clinical management of the subjects. If complications arise, the patient will still be eligible for additional PK studies unless the complication affects the pharmacology of BUP i.e. significant liver or renal disease.

If a patient who consented to any part of this study (Parts A-E) is dismissed from her Medication Assisted Treatment (MAT) clinic due to non-compliance, she will be dismissed from the study and another subject will be recruited to replace her.

If non-prescribed opiates/opioids are detected during any PK screening visits, the subject will be ineligible to complete the pending PK visit. Subjects may be re-screened at a later date as long as they are within the gestational window for the PK visit. If a subject in the PK study has two positive drug screens for non-prescribed opiates/opioids during any screening visits, she will be dismissed from the study and replaced with another study subject.

At the time of enrollment, patients will consent to those components of the study that they wish to participate in. Subjects are required to complete at least one PK study in order to participate in this portion of the study. If a subject consents to portion of the study and they are unable to complete it within the acceptable timeline, they will still be eligible to participate in the remaining

parts of the study they consented to.

D.5.iv. Study PK Visits:

Once the subject has signed the consent form, completed the Screening Visit, and is deemed eligible for the study, the research staff will establish a schedule for the subject to undergo their first PK study. Subjects participating in the PK study must complete at least one PK study.

Screening Visits will be conducted within 1-2 weeks prior to each PK study and subjects must continue to meet the criteria listed in section D.4, with the exception of exclusion criteria items 6 and 7. A urine drug screen (Immunoassay) will be performed on the day of the PK study.

Each PK study, both during and after pregnancy, will be performed after the subject has been on a consistent two, three, four, or five time daily dose of BUP for a minimum of 7 days.

D.5.v. BUP Administration During PK Visit:

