The following collection and processing instructions apply to all blood and saliva samples collected during this study. The samples collected will be dependent on which parts of the study the subject participates in.

Blood samples will be collected as follows:

- Maternal and Cord Blood Samples for BUP Analysis: One 10 mL heparinized vacutainer tube will be drawn at the time points described in sections D.5.vi and D.5.ix. The tube should be centrifuged at 1500 g at 4°C for 15 minutes. Plasma samples will then be transferred into polypropylene tubes and frozen at -80 degrees centigrade until analysis.
- PBMC analysis: One 5 mL EDTA vacutainer tube will be drawn with the first sample (pre-dose) at each PK study visit and at delivery (applicable to all subjects), when possible. The sample should be stored at room temperature. Notify [name] lab in advance at [contact] / [contact] or via email ([contact]) to allow for pick up and processing within 4 hours of collection.
- DNA Analysis: One 10 mL EDTA vacutainer tube will be drawn at the Baseline Screening Visit. If the DNA sample is unable to be obtained at the screening visit, it may be collected anytime during the study when blood is being drawn. The sample should be frozen at -80 degrees centigrade until analysis.

Saliva samples will be collected using a Sarstedt Salivette collection device. The salivary collection sponge can be centrifuged later in the day. Salivary pH will be determined. Oral fluid samples will then be transferred into polypropylene tubes and frozen at -80 degrees centigrade until analysis.

D.5.xii. Study Outcome Measures and Ascertainment (Applicable to all Subjects):

Mothers and infants will be followed until they are discharged from the hospital, at which time relevant data from the labor, delivery and nursery records will be recorded.

a. Primary Outcome:

The primary outcome is the exposure to BUP (AUC) during pregnancy and the post-partum state.

b. Secondary Outcomes Maternal:

Other maternal outcomes to be measured are:

1. The relationship between COW and Craving scores, pupillometry, heart rate, blood pressure

and GSR scores to the maternal plasma concentration of BUP and its major metabolites

2. The impact of polymorphisms of CYP 450 and conjugating enzymes of buprenorphine on plasma concentration of BUP and its major metabolites
3. The relationship between the umbilical cord and maternal concentration of BUP and its major metabolites

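### PBMC enzyme and transporter expression is to be correlated with plasma concentrations that are not adjusted for dose, although each woman takes her own symptom-titrated dose

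*Combined protocol and SAP*

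**What the plan says.** Section D.1 (For Specific Aims 2, 4 and 5) introduces PBMCs as a surrogate marker and gives one analysis for them: "The expression of drug metabolizing enzymes and transporters in the PBMCs will be correlated with the plasma concentrations of BUP and its major metabolites". Dose, dosing interval and time since the last dose are not mentioned. Under D.5.xi the PBMC tube is drawn before the dose at each PK visit and, when possible, at delivery in all subjects.

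The study does not set the dose. Section A says "Dosing is adjusted to the patient's symptomatology using the Clinical Opiate Withdrawal (COW) score", and that at the site "using COW scores to determine a dosing regimen has resulted in many women requiring doses higher than the 16 mg daily dose". D.5.iii adds "No attempt will be made to mandate clinical management of the subjects". Under D.5.v each woman brings her own medication and takes it two, three, four or five times daily.

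Two statements about SNPs have similar wording. D.1 says "We will determine the impact of the CYP and UGT SNPs on plasma and umbilical cord blood concentrations of BUP and its metabolites". Maternal secondary outcome 2 in D.5.xii reads "The impact of polymorphisms of CYP 450 and conjugating enzymes of buprenorphine on plasma concentration of BUP and its major metabolites".

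Elsewhere the plan does adjust for dose. D.2 expresses exposure as the dose-adjusted AUC, and the sample-size text in D.5.xiii uses the same measure.

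**The concern.** At steady state, average concentration is dose rate divided by apparent clearance (CL/F). If the clinic raises the dose in women who clear the drug quickly, dose and clearance move together and concentration reflects clearance less well. The protocol's own reasoning makes this plausible. Section C expects faster metabolism in pregnancy to give sub-therapeutic levels in some women, and sections A and B expect higher doses to be needed. Even without such compensation, dose differences unrelated to metabolism add noise to concentration.

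What is at stake is the judgement on PBMC expression as a surrogate. For parent BUP, a marker that tracks clearance could be set aside because its correlation with concentration is weak. For a metabolite, a correlation could appear that reflects only the dose.

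**Working it through.** The plan gives no sample size, effect size or power for the PBMC analysis, so there is no figure of its own to reproduce. What follows is an illustration.

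**Inputs from the documents.** 40 women in the PK study (D.1). CV of 50% for clearance (D.6), so the SD of ln CL is s = √ln(1 + 0.5²) = √ln 1.25 = 0.472.

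**Assumed inputs.** Expression X (standardised) explains 25% of the variance of ln CL, so b = √0.25 × 0.472 = 0.236. Residual SD of ln concentration 0.25. SD of ln dose unrelated to clearance 0.3. One observation per woman. Degree of dose compensation k from 0 (none) to 1 (complete).

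**Model for parent BUP.** With D the dose rate and CL standing for CL/F:

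- ln C = ln D − ln CL + e
- ln D = k·ln CL + d
- hence ln C = −(1−k)·ln CL + d + e

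The slope of ln C on X is −(1−k)·b. The slope of ln(C/D) on X is −b for any k.

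**Correlations.**

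- Raw: r = −(1−k)·b / √[(1−k)²s² + 0.3² + 0.25²]
  - k = 0: −0.236/√0.3756 = −0.39
  - k = 0.5: −0.118/√0.2083 = −0.26
  - k = 1: 0.00
- Dose-normalised: r = −b/√(s² + 0.25²) = −0.236/√0.2856 = −0.44

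**Power** is from the Fisher z approximation, Φ(atanh|r|·√37 − 1.96) plus the negligible opposite tail.

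| k | raw r | power | dose-normalised r | power |
|---|---|---|---|---|
| 0 | −0.39 | 70% | −0.44 | 82% |
| 0.25 | −0.34 | 57% | −0.44 | 82% |
| 0.5 | −0.26 | 36% | −0.44 | 82% |
| 0.75 | −0.14 | 14% | −0.44 | 82% |
| 1 | 0.00 | 5% | −0.44 | 82% |

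With an unrelated dose SD of 0.5 instead of 0.3, raw power is 53%, 39%, 22%, 10% and 5%. Dose-normalised power stays at 82%.

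**Metabolite.** Suppose its level follows the dose with a constant formation fraction: ln M = ln D + h, with SD of h 0.25. Then the raw correlation is r = k·b/√(k²s² + 0.3² + 0.25²), which is 0.00, 0.26 and 0.39 at k = 0, 0.5 and 1. Because ln(M/D) = h, the dose-normalised correlation is zero, so here the raw association is produced by titration alone. If expression also affects the metabolite's own clearance, the raw correlation mixes the two effects and may move in either direction.

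**Does another section repair this?** The NONMEM covariate list in D.5.xiii includes BUP dose and SNPs but not PBMC expression. The multiple regression in D.5.xiii names CYP3A4/5 expression but does not name dose.

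**The case against.** The strongest objection concerns scope. A reader might infer that Aim 2 as a whole is biased to the null and that a functional SNP would look neutral. The documents do not support that. Aim 2 names age, race, co-medications and SNPs, and asks about their impact "on the variability in exposure of BUP and its metabolites in pregnant women"; D.2 expresses exposure as dose-adjusted AUC. D.5.xiii tests these covariates in a population PK model, which takes each woman's dosing as input and estimates clearance, so titration does not remove a SNP effect there. Outcome 2 can fairly be read as a label rather than an analysis. This objection stands. What remains for SNPs is wording that could be followed literally, including for cord blood, which the description of the model does not mention.

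A reader might also infer that titration cancels the effect of expression. That needs k = 1, and the documents point to incomplete titration. Section B says that half the COW parameters are subjective, section C allows for psychological craving and sub-therapeutic levels, and D.5.v gives only two tablet strengths. This also stands: attenuation of unknown size is all that can be said.

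Three further points have some weight. The size rests on assumed inputs. The constant result after normalisation is built into a model with dose-proportional exposure. And D.3 (question 2) asks which covariates affect actual concentration, so raw concentration is of interest in its own right. None of these makes unadjusted concentration a good test of a surrogate for metabolic activity.

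**Conclusion.** The point holds for the PBMC expression analysis. As written, it relates a proposed marker of metabolic activity to a quantity that also depends on a symptom-titrated dose, and no other section supplies a dose-adjusted version. For parent BUP the slope is multiplied by 1−k and the correlation is diluted by unrelated dose differences, so under the assumed inputs dose normalisation gives higher power even at k = 0 (82% against 70%). At k = 0.5 the gap is 82% against 36%. These figures are a range, not an estimate, because k, the strength of the expression effect and the noise terms are not in the documents. For metabolites the direction is not fixed, so a general bias to the null cannot be claimed. The analysis is secondary, and D.3 already warns that some secondary questions may lack sample size, but the correction uses a measure that the plan has already adopted for its primary question.

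**What to change.** - **PK-visit samples.** Relate expression to log CL/F or log dose-normalised AUC from the same visit, and to the metabolite-to-parent AUC ratio. Alternatively, add expression to the population PK covariates.
- **Delivery samples.** These have no AUC. Use concentration adjusted for dose and time since last dose, or individual estimates from the population PK model. Record dose and last-dose time at that draw. The protocol states this recording for the screening or consent sample and for Part E, but not for delivery.
- **SNP wording.** Align the D.1 sentence and outcome 2 in D.5.xii with the population PK analysis or with dose-adjusted exposure.
- **Raw concentrations.** These correlations may stay as secondary description.

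The cost is a change of wording, a little more analysis and one added record at delivery. Dose and AUC are already obtained at each PK visit. Dose normalisation assumes roughly dose-proportional exposure, which the dose covariate already planned in NONMEM can check.

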- When possible, a small quantity of maternal and newborn hair will be removed from the scalp as close to delivery as possible for determination of buprenorphine and metabolites.
- In the nursery, the infant will undergo standard newborn testing for signs of neonatal withdrawal (Neonatal Abstinence Syndrome, NAS). The duration and intensity of treatment will be recorded.

Maternal and umbilical cord blood and maternal and infant hair concentrations of BUP and its major metabolites will be determined by mass spectrometry. We will determine maternal cord blood concentration ratios and hair concentrations of buprenorphine and related concentrations to the severity of neonatal withdrawal symptoms.

For Specific Aim 6: Subjects who are breastfeeding and undergoing the postpartum pharmacokinetic study will also be asked to provide breast milk samples for estimation of total amount of BUP and its metabolites secreted. On this PK study day, subjects will be asked to pump the breast just prior to taking the study dose of BUP. Subjects will then take the BUP dose. Approximately every 2-4 hrs. after BUP administration, breast milk will be pumped using a breast pump and total volume measured. An aliquot of at least 1 ml but no more than 5 ml will be saved for analysis of BUP and its metabolites, and the rest of the milk will be returned to the mother for feeding the baby. In those women consenting, we will also obtain one heel stick blood sample prior to a feeding and another sample 1 hour after the feeding. Optimally, this will be done during the feeding that is as close as possible to the mother's BUP dose.

We will also perform another elective ancillary study while the baby is hospitalized or during routine postpartum PRC appointments to evaluate the time of appearance of BUP in breast milk and to assess how much drug gets into the baby's blood. We will study postpartum women who are

breast feeding and will request 1-3 samples (at least 1 ml but no more than 5 ml each) of the mother's milk for analysis of BUP. We will request 2 infant heel stick samples with each breast milk collection. One heel stick sample will be collected prior to a breast feeding (trough level) and another one 1 hour after the feeding (peak level).

D.2. Primary Research Question

The primary research questions are whether BUP and metabolite exposure (reflected as the dose-adjusted AUC) differs during pregnancy and between pregnancy and the postpartum state.

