4. The relationship between maternal dose and concentration of buprenorphine and metabolites in umbilical cord, maternal and infant hair
5. The relationship between maternal plasma and breast milk concentrations of BUP and major metabolites
6. Cumulative amount of BUP and its metabolites excreted in breast milk.

c. Secondary Outcomes Neonatal:

Neonatal outcomes to be measured include the following:

1. Relationship between concentrations of BUP and its metabolites in maternal and umbilical cord plasma and maternal and newborn hair and maternal dose and parameters of neonatal withdrawal
2. Infant hospital days
3. Birthweight
4. Gestational age
5. Neonatal Complications including: Respiratory distress syndrome (RDS), stillbirth, neonatal death, intraventricular hemorrhage as determined by cranial ultrasound, bronchopulmonary dysplasia, necrotizing enterocolitis, early onset of neonatal sepsis, seizures, retinopathy of prematurity (ROP), and hyperbilirubinemia.

D.5.xiii. Statistical Considerations

Data Analysis Plan:

The primary outcomes will be the area under the plasma concentration x time curve (AUC) of BUP during early pregnancy compared to the AUC in late pregnancy. We will also compare the AUC of BUP and metabolites during early and late pregnancy and the post-partum period. Mixed-effect models, repeated measures ANOVA or paired t-testing, will be used to compare early to late-pregnancy and overall pregnancy values to the postpartum values. Secondary outcomes such as metabolite concentrations will be analyzed in the same fashion. Additional analysis will also include multiple regressions to evaluate the relationships between maternal and fetal plasma concentrations of BUP and its metabolites, placental p-glycoprotein, physiologic parameters and CYP3A4/5 expression. We will also use population pharmacokinetic analysis to evaluate the contribution of various covariates (i.e. maternal genotype, BMI, etc.) to the observed variability in the trough plasma concentrations of BUP.

Primary Hypothesis

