Based on data from our recently completed study, the dose-adjusted AUC was 2.34 ± 1.82 (ng/ml).hr in pregnant women at a mean gestational age of 34 weeks. In postpartum women, the dose adjusted AUC was nearly 100% higher at 4.0 ± 2.8 (ng/ml).hr. We anticipate that the AUC in the first half of pregnancy will be somewhere between values of non-pregnant women and those of pregnant women in the latter part of pregnancy. The sample size required to demonstrate a 50% difference between the dose adjusted AUC in the first half of pregnancy and the second half of pregnancy as well as a 50% difference between the dose adjusted AUC in the first half of pregnancy and the postpartum state is 37 ($\alpha = 0.05$, $\beta = 0.80$). We will recruit an additional 3 subjects to

account for dropouts or noncompliance. The secondary physiological outcomes will also be addressable with this sample size as the variance in pupil measurements is small (4.65 ± 0.4 mm at baseline and 2.64 ± 0.08 mm at 2 hours in the paper of Middleton et al¹³) and each patient will provide data from 2-3 PK studies. Thus there will be 120 studies that relate a physiologic variable to plasma buprenorphine. Specific Aim 5 which relates NAS to various parameters (maternal dose, maternal and cord plasma buprenorphine /metabolite concentrations etc.) can be addressed with the projected sample size as correlations between the dependent variable NAS and the numerous independent variables i.e. maternal dose, maternal concentration at delivery, maternal hair concentration, cord blood concentration, newborn hair concentration etc. can be performed with samples size of 15. We assume that 50 % of these infants will have some degree of NAS so the sample size of 40 should be sufficient. If the prevalence of NAS is lower, we can recruit additional subjects. Since the extensive PK studies will not be required to test this hypothesis, recruitment should be easier and can be done at secondary sites if needed.

Secondary Hypotheses

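### The primary question is stated inconsistently, and the sample size of 37 (5% alpha, 80% power) supports one AUC contrast, not the two claimed for it

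*Combined protocol and SAP*

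**What the plan says.** Four places in the protocol describe what is primary.

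- **D.2, Primary Research Question:** "The primary research questions are whether BUP and metabolite exposure (reflected as the dose-adjusted AUC) differs during pregnancy". The sentence continues with pregnancy against the postpartum state. This covers BUP and metabolites, dose-adjusted, over two comparisons.
- **D.5.xii, Primary Outcome:** "The primary outcome is the exposure to BUP (AUC) during pregnancy and the post-partum state". This covers BUP only, does not mention dose adjustment and names no contrast.
- **D.5.xiii, Data Analysis Plan:** "The primary outcomes will be the area under the plasma concentration x time curve (AUC) of BUP during early pregnancy", compared with late pregnancy. Postpartum comparisons are introduced as additional, metabolite concentrations are classed as secondary, and the tests listed are early against late pregnancy and overall pregnancy against postpartum.
- **D.5.xiii, Primary Hypothesis:** the sample size is given for a 50% change from early to late pregnancy and, within the same sentence, "as well as a 50% difference between the dose adjusted AUC in the first half of pregnancy and the postpartum state is 37". The stated alpha is 0.05, and 0.80 is printed as beta but can only be meant as power.

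No section says whether one difference or both are needed, gives a testing order, or divides alpha.

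**The concern.** Metabolites are primary in D.2 and secondary in D.5.xiii. The postpartum contrast that is sized (early pregnancy against postpartum) is not the one listed for analysis (overall pregnancy against postpartum). One n, at one alpha and one power, is claimed for two differences.

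Alpha and power describe a decision rule, and here there is none. Until the plan names the analyte, the contrast or contrasts and the rule, a reader of the results cannot tell what error rate or power lies behind a statement that pregnancy changes BUP exposure. The comparison put forward as primary could also be picked after the data are seen.

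**Working it through.** **Inputs.** From D.5.xiii, Primary Hypothesis: late pregnancy "the dose-adjusted AUC was 2.34 ± 1.82 (ng/ml).hr in pregnant women at a mean gestational age of 34 weeks"; postpartum "the dose adjusted AUC was nearly 100% higher at 4.0 ± 2.8 (ng/ml).hr"; a 50% difference for each contrast; alpha 0.05 (taken as two-sided); power 0.80; early pregnancy expected between the other two values, with no figure. No within-woman correlation is given anywhere.

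**1. Reproducing 37.** Take 50% of 2.34 = 1.17 as the difference and 1.82 as the SD, unpaired:

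n = 2 (z0.975 + z0.80)² (SD/δ)² = 2 × (1.960 + 0.842)² × (1.82/1.17)² = 37.98, so 38 per time point.

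Power at 37 = Φ(1.17 / (1.82 √(2/37)) − 1.96) = Φ(0.805) = 0.79.

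This is within one of the stated figure, for one contrast at the full 0.05. A log-scale 1.5-fold ratio with CV 70% also gives about 38. The 50% CV in D.6 gives only 16. A Bonferroni calculation (alpha 0.025) on 50% of 4.0 with SD 2.8 happens to give 38 too, but the text states alpha 0.05, and early against late at 0.025 would need 46.

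**2. What two contrasts do to alpha and power**, each tested at 0.05.

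| Decision rule | Type I error | Power |
|---|---|---|
| Early against late only | 0.05 | 0.79 |
| Either contrast suffices | 1 − 0.95² = 0.0975 if independent; 0.091 at correlation of size 0.5 | 0.91-0.99 for at least one, if each has 0.80 |
| Both required | at most 0.05 | Φ₂(0.842, 0.842; ρ) = 0.61, 0.64, 0.69 at ρ = −0.5, 0, 0.5, if each has 0.80 |

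For the two sized contrasts ρ = −0.5 under equal variances, because early pregnancy enters them with opposite signs. For the two contrasts listed in the Data Analysis Plan ρ = 0, because they are orthogonal under equal variances.

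**3. Pairing.** The planned tests are paired or repeated-measures. With 37 complete sets, δ 1.17 and SD 1.82 for both sized contrasts, assumed within-woman correlations of 0.25 and 0.5 give single-contrast power of 0.89 and 0.97. Joint power is then about 0.78 and 0.95 by normal approximation, or about 0.74 and 0.94 in simulation with paired t-tests. However, D.1 requires only one PK visit per woman, so 37 pairs are not assured. With 25 pairs and correlation 0.25, single-contrast power is 0.75.

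**4. Whether both 50% effects can occur.** Two successive 50% rises from 2.34 reach 1.5 × 1.5 × 2.34 = 5.27, above the postpartum 4.0. The whole late-to-postpartum gap is 4.0/2.34 = 1.71, a 71% rise.

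- If early is 3.51 (50% above late), postpartum is 4.0/3.51 = 1.14, or 14% higher, a difference of 0.49. Power at 37 is Φ(0.49 / (2.8 √(2/37)) − 1.96) = 0.11 unpaired with SD 2.8. It is 0.19 with SD 2.8 and correlation 0.5, and 0.21 unpaired with SD 1.82. Taking both favourable assumptions together (SD 1.82, correlation 0.5) gives 0.37.
- If early is at the midpoint, 3.17, each step is 0.83. Unpaired power is about 0.50 for early against late (SD 1.82) and 0.25 for early against postpartum (SD 2.8).

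**The case against.** The strongest defence is that the Data Analysis Plan already has a workable hierarchy: early against late pregnancy is primary, postpartum is additional, metabolite concentrations are secondary. On that reading alpha is 0.05 and power about 0.79, so both stated properties hold. This stands. A reader might infer that alpha or power must fail whichever definition is adopted; the documents do not support that. Nor do alpha and power fail together under any one rule.

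The 61-69% is also conditional. It fixes each contrast at 80% and takes no credit for pairing, which could restore joint power if women complete all visits. That stands too, but the plan gives no correlation to rely on and requires only one visit. Moreover, fixing both contrasts at 80% describes effects that the plan's own means rule out.

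A reader might further infer much larger error rates by counting each metabolite as primary. The documents do not say how many metabolites would be tested or how they correlate, so no figure beyond the two BUP contrasts is supported.

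Finally, D.5.xii can be read as naming a variable rather than a rival hypothesis. That softens one of the four statements. It does not reconcile D.2 with D.5.xiii on metabolites, or the sizing with the analysis on the postpartum contrast.

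**Conclusion.** The point holds in a limited form. The plan contradicts itself on what is primary, and 37 at 5% alpha and 80% power is a single-contrast figure that cannot be attached to a two-difference conclusion.

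The consequence depends on the rule eventually chosen: about 9-10% family-wise error if either BUP contrast suffices, 61-69% joint power if both are required, and little change if early against late stands alone. These figures assume two-sided tests and, for joint power, 80% on each contrast. Pairing could improve power by an amount the documents do not allow one to calculate.

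Separately, two 50% differences are incompatible with an early value between 2.34 and 4.0. If the first holds on the late-pregnancy mean, power for early against postpartum is about 0.11 to 0.21 across most of the assumptions tried, and under 0.4 on the most favourable. The stated 80% therefore cannot be carried over to that contrast.

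**What to change.** In D.2, D.5.xii and D.5.xiii:

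- Name dose-adjusted BUP AUC as the only primary analyte and move metabolites to secondary.
- Name early against late pregnancy as the single primary contrast, as the Data Analysis Plan already does. Test the postpartum comparison next, in fixed order at 0.05, only if the first is significant; this keeps the overall error at 5%. An overall three-period test placed first is an acceptable alternative.
- Use the same postpartum contrast in the sizing and in the analysis.
- Restate the 80% as applying to early against late only, and withdraw the claim that 37 also shows a 50% early-to-postpartum difference. Give the power of the chosen postpartum contrast at an early value consistent with 2.34 to 4.0.

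The cost is wording in three sections. Metabolites lose primary status, and the power quoted for the second difference falls. No extra patients are needed. By contrast, on the apparent unpaired formula with 1.17 and 1.82, keeping two contrasts with either sufficient would need 46 women at alpha 0.025, and requiring both would need about 48-51 for 80% joint power, before any allowance for dropout.
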